### **3.3.2 Inclusion criteria**

For inclusion in the study, patients must fulfil all of the following criteria:

1. Patients' parent/guardian must provide written informed consent prior to the execution of any study-related procedures.
2. Patients must be full term or have gestational age  $\geq 28$  to 44 weeks (calculated from last menstruations or ultrasound).
3. Patients must be an inpatient in the Neonatal Intensive Care Unit (NICU), special care nursery, or equivalent hospital ward at the point of study entry and will be expected to remain an inpatient for the treatment period of the study. If the patient is discharged prior to completion of the treatment phase, patients may be given the option of having at home visits for study drug administration at the discretion of the

investigator. These patients will need to be readmitted to the hospital for final study day procedures.

4. Patients must have the following observed clinical findings: any two (either individually or in any combination) of (1) apnea +/- bradycardia +/- oxygen desaturations, (2) vomiting/gagging, (3) irritability/pain at least every second feed or at least twice every eight hours, and present for at least 5 days or increasing in frequency or severity over 3 days. At least 2 of the occurrences of the above should be reproducible during the 8 hour video.
5. Patient's size and medical condition must allow for performance of all study related procedures and administration of investigational product as judged by the investigator.
6. Patients must be on a stable mode of feeding or with minimal variations in feeding as judged by the investigator for at least 2 days prior to randomization.

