**Table 3 Study objectives and endpoints**

Objective	Endpoint	Summary statistic for analysis	Analysis method
Secondary: To assess the difference between esomeprazole and placebo in the treatment of symptomatic reflux episodes of GERD	Secondary: number of GERD-related signs (oxygen desaturation, apnea, bradycardia) at baseline and at end of study via clinical assessment charts	Secondary: (a) mean percentage of patients with each GERD-related sign (ie, #patients with event divided by #randomized in a treatment group), and separately for patients having at least one of the 3 signs, at baseline and end of study by treatment group  (b) mean percentage of apnea resolution rate (ie, #patients having apnea at baseline and having no apnea at the end of study divided by #patients having apnea at baseline) by treatment group (only considering patients having apnea at baseline)	Secondary: Descriptive statistics will be provided for the endpoints of interest
	Secondary: volume and frequency of vomiting episodes at baseline and at end of study via clinical assessment charts	Secondary: (a) mean percentage of patients with small/medium/large vomiting volume at baseline and at end of study by treatment group  (b) mean change from baseline in number of vomiting episodes by treatment group	
	Secondary: volume, frequency and duration of feeding at baseline and end of study via clinical assessment charts	Secondary: (a) mean volume per feeding and mean frequency of feeding by treatment group  (b) mean total feeding volume over 24 hours per kilogram by treatment group  (c) mean feeding duration by treatment group	
	Secondary: symptom severity recorded on the Physician's Global Assessment	Secondary: mean percentage of patients with no symptom (severity = none) at the end of study by baseline severity and by treatment group	

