**Table 3 Study objectives and endpoints**

Objective	Endpoint	Summary statistic for analysis	Analysis method
Secondary: To assess the difference between esomeprazole and placebo in the treatment of other GERD-related signs and symptoms via video, pH/impedance, and cardiorespiratory monitoring	Secondary: (1) Durations of sleep, waking hours, peaceful quietness, and crying, at baseline and after treatment period  (2) Number of gagging, back arching, irritability/crying/ fussing, vomiting, apnea, bradycardia, and oxygen desaturation, at baseline and after treatment period	Secondary: (1) Mean change from baseline in percentage of peaceful quietness time by treatment group; mean change from baseline in percentage of sleep time by treatment group; mean change from baseline in percentage of crying time by treatment group (2) For each sign and symptom separately, or combined as appropriate, mean percentage of patients with sign or symptom, at baseline and after treatment, by treatment group  For each sign and symptom separately, or combined as appropriate, mean change in number of events from baseline by treatment group  Secondary: mean change from baseline in symptomatic reflux episodes associated with a reflux detected from pH/impedance by treatment group	Secondary: (1) Differences in mean change from baseline in %time will be compared between treatment groups, using ANCOVA taking baseline %time as the covariate. (2) Difference between treatment groups in %patients having no sign or symptom will be compared using a chi-square test.  Change from baseline in # events will be compared between treatment groups using ANCOVA, taking baseline # events as the covariate.  Secondary: ANCOVA, taking baseline number of episodes as a covariate, will be used for the treatment comparison
	Secondary: change from baseline in the number of symptomatic reflux episodes of GERD, as observed during video recording together with a reflux detected from pH/impedance monitoring, and GERD-related sign(s) detected from cardiorespiratory monitoring together with a reflux detected from pH/impedance monitoring, at baseline and after treatment period	Secondary: mean change from baseline in symptomatic reflux episodes associated with a reflux detected from pH/impedance by treatment group	Secondary: ANCOVA, taking baseline number of episodes as a covariate, will be used for the treatment comparison

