### **6.4 Method of statistical analysis**

The primary variable, change from baseline in number of signs and symptoms as observed in the video and detected from cardiorespiratory monitoring, will be analyzed using an analysis of covariance model (ANCOVA), taking the number of episodes at baseline as the covariate. The number of signs and symptoms at baseline, at the end of the study, change from baseline, and % change from baseline will be presented for the treatment comparison.

The secondary variables, including the number of symptomatic reflux episodes of GERD as observed from the video, together with reflux detected from pH/impedance, and GERD-related signs detected from cardiorespiratory monitoring associated with a reflux from pH/impedance monitoring, will be analyzed and presented in the same way as the primary variable.

Percent time of peaceful quietness, sleep, and crying will be summarized from video monitoring data for each patient separately, at baseline and at the end of the study. For each parameter (ie, % time of peaceful quietness, sleep, and crying) change from baseline in % time will be calculated. The comparisons between treatment groups in change from baseline will be made using ANCOVA taking baseline % time as the covariate. For each parameter, the % time at baseline, at the end of study, and change from baseline will be presented for evaluating the treatment difference.

Other GERD-related signs and symptoms (eg, gagging, back arching, irritability/crying/fussing, vomiting, apnea, bradycardia, oxygen desaturation) will also be assessed at baseline and at the end of the study via video and cardiorespiratory monitoring along with measurements from pH/impedance monitoring. The number of these events will be summed up for each patient at each time point for each sign and symptom individually or combined as appropriate. Change from baseline in number of events will be compared between treatment groups using ANCOVA, taking the baseline number of events as the covariate. Patients will also be categorized as 'having' or 'not having' the sign or symptom, individually or combined as appropriate. Difference between treatment groups in percentage of patients having no event will be compared using a chi-square test. Percentage of patients having no event at baseline as well as at the end of study will be tabulated for each treatment group separately.

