The Physician's Global Assessment will be collected at baseline and at the end of the study. A CMH test stratifying on baseline severity will be used to compare the difference between esomeprazole and placebo in the percentage patients having no symptoms. A summary table of the percentage of patients having no symptoms at the end of the study will be presented by baseline severity for each treatment group separately.

Descriptive statistics will be provided on change from baseline in number of signs and symptoms, the primary efficacy endpoint, for various sub-groups if appropriate (eg, site, age group, days on study medication). Descriptive statistics will be provided on other efficacy endpoints of interest (eg, percentage of cardiorespiratory events, percentage of apnea resolution rates, percentage on vomiting categories, pharmacodynamic parameters).

Descriptive statistics will be provided for the evaluation of the safety profile (eg, AEs, lab parameters, vital signs).

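### The chi-square test on infants free of each individual sign ignores whether the sign was present at baseline; it keeps its 5% level but loses power, and its estimate shifts when the arms are imbalanced at baseline

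*Protocol*

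**What the plan says.** Section 6.4 handles gagging, back arching, irritability/crying/fussing, vomiting, apnea, bradycardia and oxygen desaturation in two ways, each sign alone or in combination.

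- **As counts:** "Change from baseline in number of events will be compared between treatment groups using ANCOVA, taking the baseline number of events as the covariate".
- **As present or absent:** "Difference between treatment groups in percentage of patients having no event will be compared using a chi-square test". Table 3 has the same rule: "Difference between treatment groups in %patients having no sign or symptom will be compared using a chi-square test". Neither sentence names a time point; end of study is the natural reading.

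Baseline enters the present/absent analysis only as a description: "Percentage of patients having no event at baseline as well as at the end of study will be tabulated for each treatment group separately".

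For the other binary outcome with a test in section 6.4, the Physician's Global Assessment, the rule is different: "A CMH test stratifying on baseline severity will be used to compare the difference between esomeprazole and placebo". The chart-based apnea resolution rate in Table 3, which is descriptive, is restricted to infants who could resolve ("only considering patients having apnea at baseline").

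Inclusion criterion 4 (section 3.3.2) asks for "any two (either individually or in any combination) of (1) apnea +/- bradycardia +/- oxygen desaturations, (2) vomiting/gagging" and a third group, irritability or pain. No single sign is therefore required of every infant, and back arching is not an entry finding at all.

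**The concern.** For any one sign, the analysis set can mix infants who had it at baseline, in whom it had to resolve, with infants who did not have it and who say little about resolution. The chi-square test pools the two. If presence at baseline predicts presence at the end, that information is thrown away and the comparison is noisier than it need be. If the arms happen to differ in how many infants had the sign at baseline, the raw difference carries part of that gap.

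Among the between-arm efficacy tests in section 6.4, this is the only one that makes no use of baseline, and no reason is given. What is at stake is the sensitivity and readability of a set of secondary comparisons in a trial planned for 38 evaluable infants per arm.

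**Working it through.** **The plan's own figure.** Section 6.5 gives 38 per group, at least 80% power and alpha 0.05, with the SD 1.5 times the difference. Two-sided testing and 1:1 allocation are assumed. n = 2 × (1.96 + 0.842)² × 1.5² = 35.3, so 36 by the normal approximation and 37 by the t-test. Power at 38: (1/1.5) × √(38/2) − 1.96 = 0.946, which is 82.8% (81.8% by the t-test). The figure holds, but it concerns the primary count endpoint. No power is stated for the chi-square endpoint.

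**Assumptions.** The protocol gives no sign rates, so all rates below are assumed and varied. Each simulation uses 38 per arm and compares the Pearson chi-square with CMH stratified on sign present or absent at baseline, both without continuity correction.

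**1. Power, resolution improved only in infants who had the sign.** Infants without the sign at baseline are 90% free of it at the end in both arms.

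| Sign present at baseline | Free at end if present, placebo vs drug | Chi-square | CMH |
|---|---|---|---|
| 50% | 30% vs 60% | 29% | 36% |
| 50% | 20% vs 50% | 27% | 38% |
| 70% | 30% vs 60% | 46% | 54% |

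Hand check of the first row. Marginal proportions free are 0.5 × 0.3 + 0.5 × 0.9 = 0.60 and 0.5 × 0.6 + 0.5 × 0.9 = 0.75, with pooled value 0.675. The null SE is √(2 × 0.675 × 0.325/38) = 0.1075. The SE under the alternative is √((0.24 + 0.1875)/38) = 0.1061. Then (0.15 − 1.96 × 0.1075)/0.1061 = −0.57, or about 28%, close to the simulated 29%.

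**2. Power, common odds ratio of 4 in both strata.** The first column gives the placebo probability of being free at the end for infants with / without the sign at baseline. Cells show chi-square → CMH.

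| With / without | 30% present | 50% present | 70% present |
|---|---|---|---|
| 0.2 / 0.9 | 30% → 46% | 40% → 58% | 53% → 69% |
| 0.3 / 0.8 | 52% → 60% | 60% → 69% | 69% → 76% |
| 0.4 / 0.7 | 68% → 70% | 72% → 74% | 76% → 78% |
| 0.5 / 0.5 (not prognostic) | 80% → 79% | 80% → 79% | 80% → 79% |

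The gain is 2 to 18 points when baseline predicts the end state. When it does not, stratifying costs about 1 point. With weak persistence (50% present; 70% free if absent; 40% vs 60% free if present), the two tests are nearly equal: 14.3% and 14.9%.

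**3. Type I error over randomisation.** With no drug effect, both tests reject in 4.8% to 5.2% of trials in every scenario of step 2. In the setting of step 1 at 50% prevalence (30% free if present), the chi-square rejects in 4.8%.

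**4. Given an imbalance, no drug effect.** Suppose 15 esomeprazole and 23 placebo infants have the sign at baseline, with 30% free if present and 90% if absent in both arms. Expected difference = (8/38) × (0.90 − 0.30) = 12.6 points in favour of the drug. The chi-square rejects in 14% of such trials and CMH in 5%.

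**5. How often such a gap arises.** At 50% prevalence the difference in counts has SD √(2 × 38 × 0.25) = 4.36. P(gap of 8 or more, either direction) ≈ 2 × [1 − Φ(7.5/4.36)] = 8.5%. About half of that, roughly 4%, lies in the direction that mimics benefit.

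**The case against.** A reader might infer from step 4 that the chi-square test produces false positives by turning chance imbalance into a drug effect. The protocol does not support that. The comparison is randomised and the level is held at about 5%. The 14% applies only once a particular imbalance has occurred, and the opposite imbalance, equally likely, hides an effect.

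A reader might also infer that an infant without a sign at baseline is certain to be free of it at the end. Nothing in the protocol says so, and the calculations do not assume it.

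Four further points stand.

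- The same signs already have a baseline-adjusted ANCOVA on counts, and the baseline percentages are tabulated by arm, so an imbalance would be visible.
- The chi-square test may be applied to combinations of signs. For a composite of all signs, inclusion criterion 4 (findings reproducible on the 8-hour video) and exclusion criterion 1 (no total resolution on that video) mean nearly every infant has an event at baseline, so stratifying does little.
- The power gain depends on assumed rates and can be close to nil.
- Using CMH for one binary endpoint and chi-square for another is a difference of method, not a contradiction.

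What remains is that, for individual signs, a recorded and probably prognostic variable is left out of the test without a stated reason.

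**Conclusion.** The point holds as a modest improvement to a secondary analysis. As written, the test on individual signs does not use baseline presence. Its overall type I error is sound. Its power is lower than need be by about 0 to 18 points at 38 per arm, the size depending on how strongly signs persist and how common they are. Where an imbalance has occurred, the estimate is shifted in the direction of that imbalance, by about 13 points in the 15 versus 23 example.

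All these sizes rest on assumed sign rates. The direction of the power loss rests only on baseline presence predicting final presence, which is plausible given that the protocol adjusts for baseline in its other efficacy tests. It would be wrong to infer any threat to the primary conclusion: the primary endpoint is analysed by ANCOVA with the baseline count.

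**What to change.** In section 6.4 and Table 3, for individual signs and for combinations not present in nearly all infants at baseline, replace the chi-square test with a CMH test stratified on presence or absence of the same sign in the baseline 8-hour recording. Use the exact version where cells are sparse. Report the stratified risk difference with its 95% confidence interval, and state that the comparison is at end of study.

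The cost is a sentence in each place, settled before unblinding. No new data are needed, and the method is already in the protocol for the Physician's Global Assessment. The downside is about 1 point of power if baseline turns out not to be prognostic.

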## **6.5 Determination of sample size**

No relevant historical data on symptomatic episodes in this patient population was available for the sample size calculation. It was assumed that the standard deviation is about 1.5 times greater than the difference between treatment groups in number of symptomatic episodes.

Under the assumption, it would need 38 patients per group to provide at least 80% power at alpha of 0.05 to detect a difference between esomeprazole and placebo in change of symptomatic episodes from baseline.

## **6.6 Interim analyses**

No interim analysis is planned for this study. The safety subteam (See Section 6.7), however, may choose to request any analysis it feels necessary, including unblinding the data, to protect the safety of the patients in the study.

## **6.7 Data monitoring board**

There will not be a data monitoring board; however a Data and Safety Monitoring Plan will be available for this study. The Clinical Study Physician will monitor the SAEs on a continuous basis. A Drug Safety Physician will review all serious unexpected reports that are assessed by the investigator to be causally related to study drug within 15 days from AstraZeneca notification of the event. In addition, a safety subteam, consisting of the AstraZeneca Drug Safety Physician(s), Drug Safety Scientist, Clinical Study Physician, Study Delivery and other Clinical Study Team members will meet on a regular basis to review blinded study data regarding SAEs, non-serious AEs, discontinuation criteria, clinically significant laboratory data and vital signs. The safety subteam may request additional evaluations at their discretion from the site.

The safety subteam will also review any safety issues that arise from other Nexium pediatric studies. Ad hoc safety meetings will be held anytime a potential safety issue is identified. Any potential safety signals identified which might impact upon the benefit-risk of the product or protocol or lead to a change in the way the product is administered within future clinical trials or the post-marketing setting will be communicated in a timely manner to investigators and regulatory authorities.

Study therapy identity will only be unblinded during the safety data review if considered imperative. Unblinding may take place where knowledge of patient's study treatment is crucial to the definition, or progression, of a critical safety issue that may contribute to a decision regarding the continuation, or otherwise, of the study.

# **7. STUDY MANAGEMENT**

## **7.1 Monitoring**

Before first patient into the study, a representative of AstraZeneca will visit the investigational study site to:

- determine the adequacy of the facilities
- discuss with the investigator(s) (and other personnel involved with the study) their responsibilities with regard to protocol adherence, and the responsibilities of

AstraZeneca or its representatives. This will be documented in a Clinical Study Agreement between AstraZeneca and the investigator

During the study, a monitor from AstraZeneca or company representing AstraZeneca will have regular contacts with the study site, including visits to:

- provide information and support to the investigator(s)
- confirm that facilities remain acceptable
- confirm that the investigational team is adhering to the protocol, that data are being accurately recorded in the eCRFs, and that investigational product accountability checks are being performed
- perform source data verification (a comparison of the data in the eCRFs with the patient's medical records at the hospital or practice, and other records relevant to the study). This will require direct access to all original records for each patient (eg, clinic charts).

The monitor or another AstraZeneca representative will be available between visits if the investigator(s) or other staff at the centre needs information and advice.

The monitor(s) will verify data from the eCRFs against source data to ensure accuracy and completeness of documentation.

## **7.2 Audits and inspections**

Authorised representatives of AstraZeneca, a regulatory authority; or an Ethics Committee may visit the centre to perform audits or inspections, including source data verification. The purpose of an AstraZeneca audit or inspection is to systematically and independently examine all study-related activities and documents to determine whether these activities were conducted, and data were recorded, analysed, and accurately reported according to the protocol, Good Clinical Practice (GCP), guidelines of the International Conference on Harmonisation (ICH), and any applicable regulatory requirements. The investigator should contact AstraZeneca immediately if contacted by a regulatory agency about an inspection at his or her centre.

## **7.3 Training of staff**

The principal investigator will maintain a record of all individuals involved in the study (medical, nursing and other staff). He or she will ensure that appropriate training relevant to the study is given to all of these staff, and that any new information of relevance to the performance of this study is forwarded to the staff involved.

Before the first subject is entered into the study, the investigational staff will be trained to use the WBDC system by AstraZeneca personnel or delegates.

## **7.4 Changes to the protocol**

If it is necessary for the study protocol to be amended, the amendment and/or a new version of the study protocol (Amended Protocol) must be notified to or approved by each Ethics Committee, and if applicable, also the local regulatory authority, before implementation. Local requirements must be followed.

If an administrative change is required, such a change must be notified to or approved by each Ethics Committee according to local requirements.

If a protocol amendment requires a change to a particular centre's Informed Consent Form, then AstraZeneca and the centre's Ethics Committee must be notified. Approval of the revised Informed Consent Form by AstraZeneca and by the Ethics Committee is required before the revised form is used.

AstraZeneca will distribute amendments and new versions of the protocol to each principal investigator(s), who in turn is responsible for the distribution of these documents to his or her Ethics Committee, and to the staff at his or her centre. The distribution of these documents to the regulatory authority will be handled according to local practice.

